We hypothesize that administering a course of steroids to patients with Graves' or Hashimoto's thyroiditis prior to thyroidectomy will result in a less difficult thyroid operation (measured by a previously validated scale) and a lower rate of surgical complications. Furthermore, we hypothesize administering steroids will results in faster improvement in antibody levels, antibody mediated cytokine levels, and health care quality of life as measured by surveys.

Over the past 5 years, our group has performed nearly 350 thyroidectomies for Graves' or Hashimoto's thyroiditis, giving us nearly 70 potential subjects per year. We have extensive qualitative methods experience and ability to collect QoL data from our recent clinical trial on prophylactic central neck dissection for patients with differentiated thyroid cancer. We developed and validated an instrument to quantify the difficulty of thyroid surgery. This project will be a small pilot that is a non-blinded, randomized trial of patients of glucocorticoids in patients about to undergo surgery for autoimmune thyroid disease. The primary aim of this pilot is really feasibility for the definitive trial: determining willingness of participants and clinicians to

enroll, rates of follow up and response to questionnaires, and time needed for recruitment, collection of data and analysis. The specific aims are for the larger, definitive trial, but will be assessed for this small pilot.

These specific aims are:

- **Determine the benefits and safety of preoperatively administered prednisone for patients with autoimmune thyroid disease undergoing thyroidectomy on:**
 - **Difficulty of surgery^{6,10} and rates of surgical complications**
 - **Serum autoantibody levels**
- **Longitudinally assess the impact of surgical treatment on QoL in patients with autoimmune thyroid disease**

Outcomes:

- Primary
 - Thyroid difficulty Scale score
 - Autoantibody levels
 - QoL scores (12 question Short Form Health Survey [SF-12], thyroid-specific quality of life patient-reported outcome measure for benign thyroid disorders [ThyPRO])
- Secondary
 - Ultrasound doppler quantification of blood flow
 - Surgical complications (parathyroid hormone [PTH] level, recurrent laryngeal nerve [RLN] injury)

Research Design and Methods:

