- Study population = 30 patients with autoimmune thyroid conditions referred to the University of Wisconsin endocrine surgery clinic for surgical management. Patients will be invited to join the study after the decision has been made to proceed with thyroidectomy as the clinical treatment of their autoimmune thyroid disease. Once they have decided to proceed with surgery, we will describe the study rationale and the risks and benefits to enrolling. We will explain that patients will be randomized to take steroids for 1 week prior to surgery, in addition to other medications that we give all patients before surgery. If they choose not to enroll in the study, their thyroidectomy will proceed as planned. For the study, 15 patients will be treated with steroids for 1 week prior to surgery, 15 will not receive steroids. Both otherwise receive the current standard of preoperative care. We are doing a stratified randomization in blocks of four within four groups of patients, as determined by category of diagnosis (Graves' vs. Hashimoto's) and BMI (<35 vs >=35). The small block size will allow for equal numbers of control and treatment subjects even if category sizes are small.
 - Inclusion Criteria: Graves' disease or Hashimoto's disease with positive thyroid autoantibodies (Thyroglobulin Antibody [TgAb], Thyroid peroxidase antibody [TPO], Thyroid Stimulating Ig antibody [TSI], and/or Thyrotropin Receptor antibody [TRAb]). This information is found in the patient's medical record which is available at the time of surgical consultation. If a patient has not had antibody levels checked prior (this is rare), we can discuss the trial with the patient and draw the first set of clinical and research labs. If the clinical labs return that antibody levels are negative, we will inform the patient that they are not eligible to participate and will withdraw them from the study and discard the

research serum sample. All patients must first agree to undergo total thyroidectomy for their disease before they are even approached about the trial.

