- Day of Surgery: Surgeon will repeat the ultrasound in the operating room to compare area of blood flow. As part of the clinical workup, each surgeon always performs thyroid ultrasound using our GE Logiq clinic equipment, and this includes a single image using "doppler" mode to measure blood flow. Surgeons then do an ultrasound once the patient is positioned in the operating room to verify incision placement, and for study patients we will save one "Doppler" image for comparison purposes to the preop image. While the single image is unique to this study, performing the ultrasound is part of our routine clinical care and saving one additional image takes 10 seconds and confers no additional risk. There is no charge for this image and it will be uploaded with the clinical image to the radiology digital storage system for the surgeons to compare blood flow from before and after steroid administration. Research specific blood draw (15mL) will occur at the time of IV placement and sent for antibody levels. Patients will be asked whether they took their course of steroids as described and we will record their answers. If they report not taking it as directed, their narrative reasons for not doing so will be recorded. Total thyroidectomy will be performed using standard techniques in all patients potentially eligible for randomization. An open technique will be used to remove the entire thyroid including pyramidal lobe and all visible thyroid tissue. Care will be taken to visualize and preserve both recurrent laryngeal nerves and to preserve all parathyroids *in situ*. All removed specimens will be carefully examined for any parathyroid tissue and any devascularized or resected normal parathyroid glands will be confirmed by frozen section and autotransplanted into the sternocleidomastoid muscle, as per our standard of care. The surgeon will then fill out the "Thyroid Difficulty Scale" at the conclusion of the operation, either by the surgeon entering it directly into the secure RedCap project or recording their answers on paper that is coded and entered later. If on paper and coded, surgeons will store the paper separately from any PHI related to that subject and will destroy the paper as soon as it is entered into the database.

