- Given low rates of wound infection in this population, any wound infection requiring treatment with antibiotics in the steroid group will be considered an adverse event (AE) and will be investigated immediately by the principal investigator and operating surgeon, and reported to the IRB within 14 business days. If a wound infection requires an operation, it is considered a serious adverse event (SAE), although it is not immediately life threatening or debilitating to other subjects, so also will be reported with 14 business days to the IRB. If a second wound infection requiring antibiotics or surgery occurs in the steroid treated group, enrollment will immediately cease and it will be reported as a SAE in the same 14 day timeframe, when we will closely scrutinize these cases with the help of the IRB to determine whether it is safe to proceed. Monitoring for wound infections will occur in the context of our usual clinical care. We will see every wound in person at the postoperative visit, but otherwise we rely on patients self-reporting to alert clinic staff if they have concerns (redness, warmth, drainage) about their incisions. No specific study-specific instructions will be given to study subjects, we will simply ask them to call the clinic staff if they have any concerns, and clinic staff will be trained to immediately notify [name] if a study patient reports wound complications.
- Statistical Considerations: Provides an explanation as to why the number of subjects was chosen and the means for analyzing data will meet the specific aims/study objectives
 - As a small pilot, feasibility study, the size of 30 is based on our estimate of a realistic recruitment rate for the future definitive trial. We see approximately 70 potential subjects in our clinics per year, and our listed exclusion criteria are rare in our population. We estimate that fewer than one fourth will not meet criteria, and an additional one fourth may decline to participate. From the patient perspective, enrollment involves only answering QoL surveys and possibly taking a medication 1 week prior to surgery, the risks and effort are not much greater, which is why we estimate a generous rate of inclusion. We are giving ourselves 1 year to enroll all 30 patients (with an additional 6 months to collect follow up data). Our biostatistics team has already been engaged and feels this is an aggressive but realistic expectation. For all primary aims, data will be analyzed

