using a mixed model two-way analysis of variance examining the effects of the treatment group. When appropriate, t-tests comparing the steroid prep vs non-steroid prep groups will be performed. Our WISOR biostatistics core will perform this analysis using SAS statistical software. This supplemental data analysis will then be used to obtain a sample size calculation for our future study.

- There is no planned interim analyses for this short study
- The data will be analyzed in an “intent-to-treat” fashion with groups being analyzed based on their initial group and not on whether or not they report taking the steroid medication. However, if large numbers of patients report not taking the medication as directed, this is very important information for our future larger study and we will record patient responses and reasons for this.
- Drop-outs are not expected in high numbers for this population. Everyone who undergoes thyroidectomy requires levothyroxine therapy postoperatively, and we follow all of our patients very closely for at least 6 weeks. It is possible that the 6 month data will be more challenging to obtain, and that is also very important information to know in this feasibility trial.
- Data and Record Keeping: Addresses how data will be captured, protected, and shared with others
 - The Principal Investigator will manage the study data
 - Data confidentiality will be assured by coding and storing electronic data on password protected Department of Surgery servers, storing coding keys and data separately, as previously described. Data will be destroyed 10 years after publication of study findings.
- Bibliography & References Cited:

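### The primary-outcome analysis names the arms but not the second factor, model term or visit, and gives the randomisation strata and baseline values no stated role, so precision may be lost.

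*Combined protocol and SAP*

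**What the plan says.** Statistical Considerations gives one analysis for three kinds of outcome: "For all primary aims, data will be analyzed" "using a mixed model two-way analysis of variance examining the effects of the treatment group". It adds: "When appropriate, t-tests comparing the steroid prep vs non-steroid prep groups will be performed". The results have a stated use: "This supplemental data analysis will then be used to obtain a sample size calculation for our future study".

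Other sections bear on the model:

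- **Randomisation** (Research Design and Methods): "We are doing a stratified randomization in blocks of four within four groups of patients, as determined by category of diagnosis" and BMI (below 35, or 35 and above). The target is 15 patients per arm.
- **Difficulty scale** (Study Procedures, Day of Surgery): scored once, "at the conclusion of the operation, either by the surgeon entering it directly into the secure RedCap project" or on paper. It has no baseline.
- **QoL** (schedule table): preoperatively, then 6 weeks and 6 months after surgery.
- **Antibodies** (schedule table): preoperatively, then day of surgery, 2 weeks, 6 weeks and 6 months, for types positive preoperatively.
- **Aims** (Specific Aims/Study Objectives): one aim is to "Longitudinally assess the impact of surgical treatment on QoL in patients with autoimmune thyroid disease". The section also says "The primary aim of this pilot is really feasibility for the definitive trial".

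No section says what the second factor is, which term or visit carries the treatment comparison, or what part the strata and baseline values play.

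**The concern.** A two-way model needs a second factor, and time, diagnosis and BMI group would all fit the sentence. With time as the factor, the model cannot apply to the difficulty scale, which is measured once, so a t-test is the natural reading there. For QoL and antibodies the analyst could report a group main effect, an interaction, or a difference at some visit, and could use or ignore baseline.

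Two sources of precision are already in the design and have no stated use:

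- **Strata.** Stratified randomisation balances the arms on diagnosis and BMI. If these are prognostic, an unadjusted t-test still counts their variation as noise, so its standard error is too large and the test is conservative.
- **Baseline.** If preoperative QoL and antibody values predict later ones, a comparison that ignores them, or merely subtracts them, is less precise than one that adjusts for them.

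At stake are the width of the pilot's intervals and the SD handed to the definitive trial. If that trial adjusts, an unadjusted pilot SD overstates what it will face, and the error is toward a larger trial.

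**Working it through.** **The plan's own figure.** The only size given is 30, set by expected recruitment. From about 70 candidates a year, with up to a quarter ineligible and a further quarter declining, 70 × (1 − 0.25 − 0.25) = 35, or 70 × 0.75 × 0.75 = 39.4. Both exceed 30. No power is stated, so none can be reproduced or faulted.

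**Inputs.** From the documents: 15 per arm, blocks of four in four strata, and one post-baseline measurement (difficulty), two (QoL) or four (antibodies). Assumed, because the documents give none: two-sided alpha 0.05, outcome SD 1, an effect of 0.8 SD, baseline correlation ρ, strata R², 50% Graves' and 35% with BMI of 35 or more.

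**1. Strata, as they affect the difficulty scale.** With the arms balanced within strata, the true variance of the difference is (2/15)(1 − R²), while the t-test estimates about 2/15. Its 28-df critical value of 2.048 then acts like 2.048/√(1 − R²) = 2.16, 2.29 and 2.45 at R² of 10, 20 and 30%. Simulated trials with the plan's blocks and strata, R² split equally between the two factors, give:

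| Strata R² | t-test type I error | t-test power | Adjusted power |
|---|---|---|---|
| 0 | 5% | about 56% | about 56% |
| 10% | about 4% | about 56% | about 60% |
| 20% | about 3% | about 56% | about 65% |
| 30% | about 2% | about 56% | about 71% |

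The adjusted model's type I error stays near 5%.

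**2. Baseline, QoL or one antibody at one named visit.** Variance of the arm difference:

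- post-only: 2/15
- change from baseline: (2/15) × 2(1 − ρ)
- baseline-adjusted: (2/15)(1 − ρ²)

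Relative to baseline adjustment, post-only keeps 1 − ρ² of the information. Change keeps (1 − ρ²)/[2(1 − ρ)] = (1 + ρ)/2.

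| ρ | Post-only keeps | Change keeps | Post-only power | Change power | Baseline-adjusted power |
|---|---|---|---|---|---|
| 0 | 100% | 50% | 56% | 32% | 54% |
| 0.3 | 91% | 65% | 56% | 43% | 59% |
| 0.5 | 75% | 75% | 56% | 56% | 67% |
| 0.7 | 51% | 85% | 56% | 77% | 82% |

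The adjusted powers are simulated and include the cost of estimating the slope. A mixed model with baseline as a response and equal baseline means has the same variance as baseline adjustment: 0.133, 0.121, 0.100 and 0.068 SD² at the four ρ values. The change contrast has 0.267, 0.187, 0.133 and 0.080. These assume complete data and equal correlation between visits.

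**3. A group main effect that averages in baseline.** With K later visits and a constant effect, the main effect is K/(K + 1) of the true one: 2/3 for QoL and 4/5 for antibodies. An effect of 0.8 SD becomes 0.8 × 2/3 = 0.53 or 0.8 × 4/5 = 0.64.

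**4. Planning the definitive trial.** For 0.5 SD and 80% power, n per arm = 2(1.960 + 0.842)²/0.5² = 62.8, so 63. If that trial adjusts for strata, multiplying by 1 − R² gives 57, 51 and 44 at R² of 10, 20 and 30%. Sampling error is larger: a variance on 28 df has a 95% interval of 0.63 to 1.83 times its estimate, so 63 could be about 40 (63 × 0.63) to 115 (63 × 1.83).

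**The case against.** The strongest reply is that this is a feasibility pilot with a size set by recruitment. A biostatistics core will run the analysis, and the adjusted SD can be computed from the same 30 patients when the next trial is designed. A loss also needs a chain of conditions: the strata or baseline must be prognostic, the analyst must take the less efficient reading, and the definitive trial must adjust. All of that stands, and it limits the severity.

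Some stronger readings are tempting but go beyond the text:

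- **That no contrast is given.** The t-test sentence names steroid prep against non-steroid prep. What is missing is the model term and the visit.
- **That a group-by-time model forces a change-from-baseline comparison.** It does not. The same model can give the arm difference at a named visit, which with complete data and separate cell means equals the post-only difference. The change figures describe one permitted choice.
- **That the comparison is biased.** Under randomisation the post-only and change comparisons are both unbiased. Only a main effect averaging in baseline would shrink a constant effect, and the plan does not say that it will use one.

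The baseline also needs care. Research Design and Methods places the first QoL survey before the study begins, and the schedule places it at the clinic visit 2-4 weeks before surgery. The preoperative-testing text in Study Procedures requires only completion before surgery. Under that wording a survey could follow open assignment or fall within the prednisone week, and adjusting for it would then be unsafe. For antibodies, later draws at laboratories of the patient's choosing could lower ρ and shrink the gain.

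**Conclusion.** The point holds as a minor, cheap improvement. The plan leaves the second factor, model term and visit unstated and assigns no role to the strata or baseline values. A strata- and baseline-adjusted model is a better default than the stated t-test and uses only scheduled data.

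With 15 per arm and 0.8 SD, power rises from about 56% to 60-71% for strata R² of 10-30%, or to 59-82% for ρ of 0.3-0.7 at one visit. If neither is prognostic there is no gain and a small cost. Every size rests on the assumed alpha, effect, ρ, R² and stratum shares. The direction rests only on the strata or baseline being prognostic.

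A reader might infer that 30 is too few, that a stated power is wrong, or that the definitive trial will be mis-sized. The documents do not support these: there is no power claim, feasibility is the primary aim, any planning error of this kind is conservative and recoverable, and sampling error in the SD is larger.

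**What to change.** State the analysis per outcome in Statistical Considerations:

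- **Difficulty scale:** linear model with treatment, diagnosis and BMI stratum.
- **QoL and antibodies:** mixed model with treatment, visit, treatment by visit, BMI stratum, and diagnosis where both diagnoses are represented. Include the baseline value either as a covariate or as a response with equal baseline means. Fit antibodies by type among patients positive preoperatively. Report the arm difference at a named visit with its 95% CI.
- **Baseline:** use only values obtained before assignment and before any prednisone, and reconcile the passages on survey timing in Study Procedures and Research Design and Methods.
- **Planning and supportive analyses:** report the adjusted residual SD with its CI. Keep the unadjusted t-tests and the longitudinal pre-to-post QoL analysis as supportive. The version with baseline as a response also yields the latter.

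The cost is wording, no new data, and two or three of 28 degrees of freedom. If nothing is prognostic, power for 0.8 SD falls by about 1-4 points (for example 53% against 56% with baseline and both strata). In an antibody subset of 15 patients, adjusting for baseline and BMI gives 26, 27, 33 and 44% at ρ of 0, 0.3, 0.5 and 0.7, against about 29% for the t-test: a slight loss at ρ of about 0.3 or less, and a gain from about 0.5.
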